5.2.2. Analysis Population

The following populations will be used for data analyses and/or presentation.

5.2.2.1. Modified Intent-to-Treat (mITT) Population

All ITT subjects (who receive at least one dose of study drug), who have baseline and at least one post-baseline measurement for the primary endpoint. This will be the primary population for the efficacy analyses; unless specified otherwise, the mITT will be the default analysis set in this study.

5.2.2.2. Safety Population

All subjects who received at least one dose of study drug. Treatment classification will be based on the actual treatment received. This will be the primary population for the safety analyses.

The primary analysis set is the modified Intent-to-Treat (mITT), which will include all enrolled subjects who have received at least one dose of study drug. Unless specified otherwise, the mITT will be the default analysis set in this study.

5.2.3. Analysis Windows and Baseline

The observational period for the study includes the screening period (Day -28 to Day -1), treatment and follow up period (Day 1 to Day 180), additional follow up period (up to Day 300, subject will continue in the study until the observed LDL-C reduction is less than 20 % of the absolute reduction from baseline to Day 90). Any event occurring beyond the defined observational period, even if collected on the CRF, will not be included in the planned statistical analysis. However, all data, including that reported after the defined observational period, will be included in the subject data listings.

Unless otherwise specified, for evaluations that are collected at multiple occasions prior to initiation of study drug administration, the latest evaluation will be considered the "Baseline" evaluation for analysis.

5.2.4. Missing data handling

Unless otherwise specified, missing data will not be imputed and will be excluded from the associated analysis.

5.3. Statistical Analyses

5.3.1. Demographic and Baseline Characteristics

Subject demographics (age/age group, gender, weight, height, body mass index, race, ethnicity, and country) and confirmation on HoFH (yes, no) at baseline will be summarized using the mITT and safety populations.

5.3.2. Medical History

Medical history(targeted and other medical history) data collected in the eCRFs will be summarized using the mITT and safety populations.

5.3.3. Protocol Deviation

Subjects with protocol deviation(s) will be listed.

5.3.4. Study Drug Exposure

Study drug administration including actual dose injected, time for injection, and missed doses will be listed.

5.3.5. Concomitant Medications

Summary of concomitant (Day 1 or later) medication will be provided. [Medication will be coded with WHO drug dictionary]. Subjects will be counted only once within each period by medication. A listing for all prior (pre Day 1) and concomitant medications will be provided.

5.3.6. Efficacy Analysis

5.3.6.1. Primary Efficacy Endpoints

The primary endpoint is the percent change in LDL-C following 90 and 180 days of treatment.

Summary statistics and 95% CI of this primary endpoint will be provided. Changes of LDL-C from Day 1 by scheduled visits will also be summarized. Response rate of subjects with 15% or greater reduction in LDL-C from Day 1 following 90 and 180 days of treatment will be calculated.

The analysis for the primary endpoint will be descriptive. Means and confidence intervals will be provided. Mean plots with standard error bars will be provided for observed LDL-C value, change in LDL-C value, and percent change in LDL-C value.

5.3.6.2. Secondary Efficacy Endpoints

Analyses of secondary efficacy endpoints will be similar to the primary analysis of the primary endpoint.

The secondary endpoints of this trial are:

- Change and Percentage change in LDL-C from Day 1 to each subsequent visit until Day 180 or final visit
- Change and Percentage change in PCSK9 from Day 1 to each subsequent visit until Day 180 or final visit
- Change and Percentage change in total cholesterol, triglycerides, HDLC, non-HDL-C, VLDL-C, Apo-A1 Apo-B and Lp(a) from Day 1 to each subsequent visit until Day 180 or final visit

5.3.6.3. Exploratory Efficacy Endpoints

The exploratory endpoints of this trial are:

- Formation of Anti-drug antibodies (ADA) to inclisiran
- Response of LDL-C by the causal genetic mutations of HoFH

5.3.7. Safety Analysis

Safety summaries will include the incidence of adverse events, summaries of laboratory parameters (including shift tables), vital signs, ECGs and anti-drug antibodies.

5.3.7.1. Adverse Events

The Medical Dictionary for Regulatory Activities (MedDRA) dictionary will be used for coding AEs. An AE (classified as preferred term) occurring during the treatment period will be counted as a treatment emergent AE (TEAE) either if it is not present at day 1 or if it is present at day 1 but increased in severity during the treatment period.

[figure not shown]
The number (percentage) of subjects reporting TEAEs/Serious TEAEs will be tabulated by system-organ class, and preferred term. If more than one event occurred with the same preferred term for the same subject, the subject will be counted only once for that preferred term.

Subject listing on AEs/SAEs/AEs leading to a discontinuation or death will be presented.

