10.4.4.1. Adverse Events

The Medical Dictionary for Regulatory Activities (MedDRA) will be used for coding adverse events (AEs). An AE (classified by preferred term) occurring during the study drug treatment period will be counted as a treatment emergent AE (TEAE) either if it is not present at baseline or if it is present at baseline but increased in severity during the treatment period.

The number (percentage) of subjects reporting TEAEs for each preferred term will be tabulated by system-organ class, by system-organ class and severity, and by system-organ class and relationship to study drug. If more than one event occurred with the same preferred term for the same subject, the subject will be counted only once for that preferred term using the most severe or related occurrence for the summary by severity, or relationship to study drug, respectively.

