1.4. Schedule and Sequence of Procedures

The Schedule of Events/Assessments ([Table 1](#)) summarizes the study assessments by time point. This study consists of four periods: Screening, Treatment, End of Study and Additional Follow-up.

- The Screening period occurs prior to administration of study drug and consists of confirming eligibility.
- The Treatment period occurs from the time of enrolling the subject, collecting Day 1 assessments and study drug administration through Day 90/104.
- The End of Study visit occurs at Day 180.
- The Additional Follow-up period (if necessary) occurs from end of study through Day 300.
- The maximum duration of a subject's participation is from screening/informed consent to end of study (last follow-up) and is expected to be up to 328 days.

Schedule of Assessments

Table 1: Study Design and Schedule of Assessments

Study Day	Screening	Treatment Phase								End of Study (EOS)	Additional Follow-Up ^p
	-28 to -1	Day 1	FU1 Day 14 (± 2d)	FU2 Day 30 (± 3d)	FU3 Day 60 (± 3d)	FU4 Day 90 (± 3d) Dose 2? ^a	FU4X Day 104 (± 3d) Dose 2? ^a	FU5 Day 120 (± 3d)	FU6 Day 150 (± 3d)	FU7 Day 180 (± 3d)	FU8 (Day 210) (± 3) FU9 (Day 240) (± 3) FU10 (Day 270) (± 3) FU11 (Day 300) (± 3)
Informed consent	X										
Medical History and prior meds	X										
Physical Examination & full neurologic exam	X									X	
Inclusion / Exclusion Criteria	X	X									
Pharmacogenetic sample ^o	X										
Enrollment		X									
Vital Signs ^b	X	X	X	X	X	X	X	X	X	X	
12 Lead ECG ^c		X								X	
Hematology, Coagulation ^{d, f}	X	X	X	X	X	X	X	X	X	X	X
Biochemistry, Inflammatory markers ^{d, f}	X	X	X	X	X	X	X	X	X	X	X
HbA1c	X	X				X				X	X ⁿ
Urinalysis ^{e,}	X	X ^g								X	X
Pregnancy test ^{e, h}	X	X ^h	X	X	X	X ^h	X ^h	X	X	X	X ⁱ

ADA antibodies^j		X _{j, k}		X					X _k	X _k	X _k
Lipids / lipoproteins^m	X	X	X	X	X	X	X	X	X	X	X
Biomarker (stored samples)^q	X	X	X	X	X	X	X	X	X	X	X
Study drug admin		X				X ^a	X ^a				
Concomitant medications	X	X	X	X	X	X	X	X	X	X	X
AE reporting		X	X	X	X	X	X	X	X	X	X
SAE reporting		X	X	X	X	X	X	X	X	X	X

ADA = anti-drug antibodies; AE = adverse event; ECG = electrocardiogram; FU=follow-up; EOS = end of study; hsCRP=high sensitivity C-reactive protein; IL6=interleukin 6; IFN-γ=interferon gamma; LDL-C = low-density lipoprotein cholesterol; PCSK9 = proprotein convertase subtilisin/kexin type 9; SAE = serious adverse event; TNF-α=tumor necrosis factor alpha.

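### TEAEs are limited to a treatment period with no stated end day; the only explicit definition of that term stops at Day 90/104, and other sections point to Day 150, Day 180 or later

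*SAP*

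**What the plan says.** The TEAE rule is in SAP 5.3.7.1: "An AE (classified as preferred term) occurring during the treatment period will be counted as a treatment emergent AE (TEAE". Protocol 10.4.4.1 words it as "An AE (classified by preferred term) occurring during the study drug treatment period will be counted as a treatment emergent AE (TEAE". Neither section gives an end day or refers to a section that does.

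Four other places bear on where the period ends:

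- **SAP 1.4**, with identical wording in protocol 6: "The Treatment period occurs from the time of enrolling the subject, collecting Day 1 assessments and study drug administration through Day 90/104". This is the only explicit definition of the term.
- **The schedule of assessments** (SAP Table 1, protocol 6.1): the Treatment Phase heading appears to span Day 1 to FU6 (Day 150), just before the End of Study column. The column span is read from extracted text.
- **SAP 5.3.6.1**: "The primary endpoint is the percent change in LDL-C following 90 and 180 days of treatment".
- **SAP 5.2.3**: the main period is the "treatment and follow up period (Day 1 to Day 180", with additional follow-up to Day 300 for some subjects. Only events beyond the whole observational period are excluded from the planned analysis.

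On outputs, SAP 5.3.7 states "Safety summaries will include the incidence of adverse events". The only AE frequency tables that SAP 5.3.7.1 specifies are for TEAEs and serious TEAEs. The protocol's version is "The number (percentage) of subjects reporting TEAEs for each preferred term will be tabulated by system-organ class, by system-organ class and severity", and also by relationship, so it uses the same flag. The listings are wider: "Subject listing on AEs/SAEs/AEs leading to a discontinuation or death will be presented".

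**The concern.** A programmer who looks up the treatment period finds one definition, and it closes on the day of any second injection. Applied as written, it removes later events from every AE frequency table, although AE and SAE reporting is scheduled at Days 120, 150 and 180.

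Tolerability is part of the primary hypothesis (SAP 5), and safety is a secondary objective (SAP 1.2). The protocol describes a long-acting drug: in Phase I the average LDL-C reduction was still about 40% at 140 days after treatment (protocol 1.2.2), and a significant effect remained at 180 days (protocol 1.3). A cut at Day 90/104 would therefore tabulate harm over a shorter window than benefit, which is assessed to Day 180.

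Injection site reactions are the only AE of special interest, and they have no table of their own in the SAP text. One that starts after the day of a Day 104 injection would be listed but not tabulated.

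**Working it through.** The plan states no figure on this point, so there is none to reproduce. The check is day and visit arithmetic on nominal study days, without the visit windows.

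**Inputs.** Treatment period ends Day 90 or 104 (SAP 1.4, protocol 6). Apparent end of the Treatment Phase heading is Day 150 (SAP Table 1). Main period ends Day 180 and additional follow-up ends at most Day 300 (SAP 5.2.3). A second dose, if given, falls on Day 90 or 104 (SAP 1.1). n = 8 to 10 (SAP 5).

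**1. Days to Day 180 outside the TEAE window** = (180 − end) / 180.

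| Window ends | Days outside | Share |
|---|---|---|
| Day 90 | 180 − 90 = 90 | 90/180 = 50.0% |
| Day 104 | 180 − 104 = 76 | 76/180 = 42.2% |
| Day 150 | 180 − 150 = 30 | 30/180 = 16.7% |
| Day 180 | 0 | 0% |

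For a subject followed to Day 300, the Day 90 and Day 104 ends leave out 210/300 = 70.0% and 196/300 = 65.3%.

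**2. Scheduled AE-reporting visits after Day 1, up to Day 180, that fall after a Day 90/104 cut.**

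- No second dose (no Day 104 visit): FU5, FU6 and FU7, so 3/7 = 42.9%.
- Second dose, end Day 104: 3/8 = 37.5%.
- Second dose, end Day 90: the Day 104 visit is also outside, so 4/8 = 50.0%.

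**3. Time after a second dose, if one is given.**

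- Dose on Day 90: 180 − 90 = 90 days remain to Day 180. With an end at Day 104, 104 − 90 = 14 days are inside and 76 (84.4%) outside. With an end at Day 90, all 90 (100%) are outside.
- Dose on Day 104: 180 − 104 = 76 days remain, and all 76 (100%) are outside.
- So 0 to 14 days after the dose are inside the window.

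**4. Effect on a table row.** One subject whose first event of a preferred term starts after the cut lowers that row by 1/10 = 10.0 points (n = 10) to 1/8 = 12.5 points (n = 8).

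**5. Does another section settle the window?** No. SAP 5.2.3 says which events leave the planned analysis altogether, not which of the remaining events are treatment-emergent. Its observational period also includes screening, so it cannot itself be the TEAE window. Its main period names treatment and follow-up jointly and does not say where one stops. The endpoint wording in SAP 5.3.6.1 gives assessment times after one or two injections. The schedule heading gives a further candidate end.

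The documents give no AE rate for this population, so no expected number of lost events is calculated.

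**The case against.** The best case against is that nobody would apply SAP 1.4 this way. Its four periods are an outline of visits and dosing: after Day 104 nothing is named until the End of Study visit at Day 180, so Days 105 to 179 belong to no period. SAP 5.3.7.1 uses the term in lower case without pointing to SAP 1.4. SAP 5.2.3, the section on analysis windows, excludes only events beyond the observational period, which suggests that later events are meant to count. Every AE is listed, and with 8 to 10 subjects a reader can see them all.

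Most of this stands. It makes the Day 90/104 reading possible, not compelled. It does not supply an end day, and a listing does not give the incidence that SAP 5.3.7 promises.

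Three stronger readings are tempting, and the documents do not support them:

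- **That the plan deliberately discards later AEs.** The SAP 5.2.3 rule points the other way, and the listings keep the events.
- **That the Day 1 to Day 180 label contradicts SAP 1.4.** A joint label for treatment and follow-up is compatible with treatment ending earlier.
- **That protocol 8.3.1 and 8.3.2 contradict the AE and SAE reporting scheduled at FU8 to FU11.** They collect events up to EOS. Protocol 6 places the End of Study visit at Day 180 but also equates end of study with last follow-up, at up to 328 days (28 + 300). This is an ambiguity in EOS, not a proven conflict.

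**Conclusion.** The point holds as an undefined analysis window whose only explicit definition gives a poor result. If the Day 90/104 definition is used, the tables omit events starting in 42% to 50% of the time to Day 180 and in all but 0 to 14 days after any second dose. If Day 180 is used, they omit none of it. The SAP does not state the choice.

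These figures are shares of calendar time on the literal reading, not estimates of lost events, and those about a second dose apply only if one is given. The harm is limited: the trial is a descriptive single-arm pilot, all AEs are listed by subject, and the Safety Committee's ongoing review is not tied to these tables. It should still be fixed, because the change is small and, if made before database lock, avoids a later choice of which events count.

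SAP 8 cites a Netherlands-specific Amendment 2.0 that is not among the documents reviewed. Whether it changes any of these sections is unknown.

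**What to change.** - **SAP 5.3.7.1:** define a TEAE as an AE that starts or worsens from the first injection through the Day 180 visit (FU7, with its ±3-day window), irrespective of the Treatment period label in SAP 1.4.
- **Additional follow-up:** tabulate AEs that start after the Day 180 visit and up to Day 300 separately, with the number of subjects followed as the denominator, since only some subjects continue.
- **SAP 7:** record the clarification. Align protocol 10.4.4.1 at the next amendment.
- **Protocol 8.3.1 and 8.3.2:** state whether EOS means the Day 180 visit or the last follow-up, so that AE and SAE collection matches the reporting scheduled at FU8 to FU11.

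The cost is one or two sentences in the SAP, a note in section 7 and one small extra table. AE data to Day 180 are collected under either sense of EOS, so the main table needs no new data. The table to Day 300 depends on settling EOS first. The protocol wording needs IRB/EC approval and can wait for the next amendment. Tabulated TEAE counts may be higher than under a Day 90/104 cut.

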5.3.7.2. Laboratory Tests

Laboratory values will be summarized, including changes and percent changes from baseline at each time point. Analyses will also be performed for pertinent lab parameters ([Appendix 1](#)) for incidence rates of potentially clinical significant values for subjects without potentially clinical significant value at baseline.

In addition, subjects with clinically significant laboratory values ([Table 3](#)) will be listed.

5.3.7.3. Vital Signs

Change from baseline in vital signs will be summarized descriptively at each scheduled time point.

6. COMPUTER METHODS

Statistical analyses will be performed using SAS (version 9.2 or later version).

7. CHANGES TO ANALYSES SPECIFIED IN THE PROTOCOL

There are no changes to the analyses specified in the protocol.

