3.2. AE Severity

The severity of an AE will be assessed by the investigator. The investigator should ensure that any subject experiencing an AE receives appropriate medical support until the event resolves.

Adverse events will be graded on a 3-point scale and reported as indicated on the case report form. The intensity of an AE is defined as follows:

- 1 = Mild: Discomfort noticed, but no disruption to daily activity.
- 2 = Moderate: Discomfort sufficient to reduce or affect normal daily activity.
- 3 = Severe: Inability to work or perform normal daily activity.

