5.2. General Statistical Considerations and Definitions

5.2.1. General Statistical Methods

All study-collected data will be summarized by treatment group using descriptive statistics, graphs, and/or raw data listings. Categorical variables will be summarized using counts and percentages. Percentages are based on the number of subjects in the analysis set for whom there are non-missing data, unless otherwise specified. Continuous variables, including changes from day 1, will be summarized using descriptive statistics (n, mean, standard deviation [SD], median and interquartile range [first and third quartiles], minimum and maximum). All summaries are presented for all subjects due to the small sample size in this study.

The Statistical Analysis Plan (SAP) will be finalized before database lock.

Statistical analyses will be carried out using SAS statistical analysis software version 9.2 or higher (SAS Institute, Inc., Cary, North Carolina, USA).

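### SAP 7 declares no changes, but against protocol Amendment 1.0 the SAP omits the TEAE tables by severity and by relationship, and four smaller safety and medication differences go undeclared

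*SAP*

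**What the plan says.** SAP 7 consists of one statement: "There are no changes to the analyses specified in the protocol". SAP 8 names two protocol versions, Amendment 1.0 of 7 November 2016 and a Netherlands-specific Amendment 2.0 of 18 April 2017. The supplied protocol carries the Amendment 1.0 date.

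On adverse events, protocol 10.4.4.1 asks for TEAE counts and percentages by system-organ class and then, additionally, "by system-organ class and severity, and by system-organ class and relationship to study drug". A subject with repeated events under one preferred term counts once, "using the most severe or related occurrence for the summary by severity, or relationship to study drug, respectively".

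SAP 5.3.7.1 says: "The number (percentage) of subjects reporting TEAEs/Serious TEAEs will be tabulated by system-organ class, and preferred term". For repeated events, "the subject will be counted only once for that preferred term", and the rule ends there. The section then adds: "Subject listing on AEs/SAEs/AEs leading to a discontinuation or death will be presented".

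The SAP still defines both attributes. In SAP 3.2, "Adverse events will be graded on a 3-point scale and reported as indicated on the case report form", and SAP 3.3 gives two causality categories. SAP 5.2.1 makes a general commitment: "All study-collected data will be summarized by treatment group using descriptive statistics, graphs, and/or raw data listings".

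**The concern.** A section on changes lets a reader rely on the SAP without comparing it line by line with the protocol. Here that reliance would mislead. Someone who follows the SAP exactly would not produce two safety tabulations that the protocol promises, and SAP 7 would give no hint that they had gone.

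Those two tabulations separate mild from severe events and events with a reasonable possibility of drug causation from those without. Safety and tolerability is a secondary objective (protocol 2.2, SAP 1.2), good tolerability is part of the primary hypothesis (protocol 10, SAP 5), and the safety data feed the Phase III decision (SAP 1.1). An incidence table by class and preferred term cannot show either distinction.

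**Working it through.** No arithmetic beyond counting applies, and the documents give no figure to reproduce. The check sets the analysis sections of protocol Amendment 1.0 beside the matching SAP sections.

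| Item | Protocol | SAP | Result |
|---|---|---|---|
| TEAEs by class and preferred term | 10.4.4.1: planned | 5.3.7.1: planned | kept |
| TEAEs by class and severity | 10.4.4.1: planned | not named | omitted |
| TEAEs by class and relationship | 10.4.4.1: planned | not named | omitted |
| Serious TEAEs by class and preferred term | not in 10.4.4.1 | 5.3.7.1: planned | added |
| Incidence of potentially clinically significant lab values | 10.4.4.2: every parameter | 5.3.7.2: parameters called pertinent, in Appendix 1 | narrowed |
| Vital signs | 10.4.4.3: change and percent change | 5.3.7.3: change only | percent change omitted |
| Prior medication | 10.4.2: summary | 5.3.5: listing only | summary replaced |

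**TEAE tabulations.** The protocol has 3. The SAP keeps 1 and omits 3 - 1 = 2. It adds 1 of its own.

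**Counting rule.** Both documents count a subject once per preferred term. The protocol's further clause picks the most severe or related occurrence for the two extra tables. It disappears with them, so it belongs to the same omission.

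**All differences in the table.** 2 omitted AE tables + 1 added AE table + 1 narrowed lab analysis + 1 omitted vital-sign measure + 1 replaced medication summary = 6. Declared in SAP 7: 0.

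**Does another SAP section restore the two tables?**

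- SAP 5.3.7 promises AE incidence in general terms and does not mention severity or relationship.
- SAP 5.2.1 can be met by listings alone, because it offers statistics, graphs and listings as alternatives.
- The small-sample remark in SAP 5.2.1 explains why summaries pool all subjects. It does not address severity or causality.
- SAP 3.2 and 3.3 define how the attributes are assessed, not how they are reported.
- The listing sentence in SAP 5.3.7.1 does not say which attributes the listings carry.

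No supplied SAP section plans either table.

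**The case against.** The best case for the SAP is practical. In one arm of 8-10 subjects, severity and relationship tables will mostly hold zeros and ones, and a listing by subject is the more detailed source. Severity and causality are still collected, so nothing is lost at source and the tables could be made later. Neither document sets a severity or causality threshold for calling the drug well tolerated. All of this stands. It limits the importance of the point and makes listings only a legitimate choice. It does not make SAP 7 accurate, because that choice is a change and is not declared.

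A second argument is that SAP 7 refers only to the protocol, that SAP 8 cites two versions, and that one of them was not supplied. This properly limits the claim to Amendment 1.0. Whatever a country-specific amendment says, the statement is still wrong against the other version that the SAP cites.

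A third argument is that a three-column severity table does not say what to do with injection site reactions, which SAP 3.6 grades I to V by CTCAE. That is fair, and the fix has to cover it.

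A reader might infer more than the documents support:

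- That severity and causality will vanish from the report. They may well appear in the AE listings; the SAP just does not say so.
- That the shortened counting rule is a separate loss. The dropped clause only serves the two omitted tables, and the general rule is intact.
- That the efficacy conclusions are at risk. SAP 5.3.6.1 keeps the protocol's LDL-C summaries, confidence interval and response rate.

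**Conclusion.** Against protocol Amendment 1.0, the no-changes statement in SAP 7 is incorrect. Two of three protocol TEAE tabulations are omitted and one is added. Three smaller differences, in laboratory values, vital signs and prior medication, are also undeclared.

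The consequence is modest. It is limited to safety and medication reporting in a descriptive pilot; AE incidence tables and listings remain, and no primary-endpoint analysis is affected. It is still more than a clerical slip, because planned output on the safety and tolerability objective goes missing without notice.

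The conclusion rests on two conditions. The comparison is with Amendment 1.0 alone. The text of SAP Appendix 1 was not among the supplied pages, so the laboratory narrowing is established from the wording, and how many parameters fall away cannot be stated. Confidence in the text comparison is high.

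**What to change.** In SAP 5.3.7.1:

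- Restore TEAEs by system-organ class and severity and by system-organ class and relationship to study drug, with the protocol's most-severe or related counting rule.
- Use the 3-point scale for all adverse events, and show the CTCAE grade of injection site reactions separately.
- State that the AE listings show severity and causality for each event.

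If the sponsor prefers listings only at this sample size, SAP 7 should declare the removal of the two tabulations and give the reason.

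In either case, replace the present sentence in SAP 7 with a list of every difference that remains: the added serious-TEAE table, the narrowed laboratory analysis, the omitted vital-sign percent change, and the prior-medication summary turned into a listing. Where one of these follows a particular amendment, name it.

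The cost is two small tables (three severity columns, two causality columns) on 8-10 subjects from data already collected, a separate display of injection-site grades, one sentence on listing contents, and a few lines in SAP 7. No new data are needed.
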